#### • Permitted concomitant medications:

Concomitant medicines are defined as any medicines taken during the treatment period (i.e., between the date of the first dose of study drug in the treatment period and the date of the last dose of study drug in the treatment period, inclusive). Any medicines started after the date of last dose of study drug will not be considered concomitant medicines. Both prior and concomitant medicine use will be summarized by the number and proportion of patients in each treatment group receiving each medicine within each therapeutic class. Concomitant medicine will be summarized for the treatment period using the Safety Population.

#### 9. ADVERSE EVENTS

#### 9.1. Adverse Events (clinical)

At each assessment, all adverse events, whether previously known or not, will be recorded with their description, intensity (severity), action taken, duration, outcome and opinion about causal relationship to the study drugs. In case of any specific Medical events of Special interest, these shall be mentioned with all required details.

## 9.2. Adverse Events (laboratory and others)

Any clinically significant change in any of the lab parameters evaluated at the end of the study or during the study conduct would be recorded as an investigational adverse event.

#### 9.3. Collection of Adverse Events

It is the responsibility of the Investigator to collect all AEs (both serious and non-serious) derived by spontaneous, unsolicited reports of subjects, by observation and by routine open questionings e.g., "How has you felt since I last saw you?"

#### 9.4. Definitions

An AE is any untoward medical occurrence that occurs in a subject or clinical investigation subject administered a pharmaceutical product, and which does not necessarily have to have a causal relationship with this treatment. An AE can therefore be any unfavorable and unintended sign (including abnormal laboratory finding), symptom, or disease temporally associated with the use of an investigational product, whether or not considered related to the product.

All AEs, including concurrent illnesses, occurring during the study will be documented in the subject's Case Report Form (CRF). Concomitant illnesses, which existed before entry into the study, will not be considered AEs unless they worsen during the treatment period. All AEs, regardless of the source of identification (e.g., physical examination, laboratory assessment), must be documented.

Pre-existing conditions will be recorded in the subject's Screening Case Report Form (CRF) on the Medical History page.

A treatment-emergent AE (TEAE) will be defined as an AE that begins or that worsens in severity after at least one dose of study drug has been administered.

#### 9.5. Assessment of Adverse Events

Each AE will be assessed by the Investigator with regard to the following categories.

#### 9.5.1. Seriousness

A 'serious' adverse event is one that is fatal or life threatening, lead to permanent disability, or requires hospitalization.

Serious events fall under the criteria as below:

- Results in death
- Is life-threatening\*
- Requires inpatient hospitalization or prolongation of existing hospitalization

- Results in persistent or significant disability/incapacity or
- Causes a congenital anomaly/birth defect
- Medically significant events (or) Important Medical events (IME)

\*A `life-threatening' adverse event places the subject at immediate risk of death in the judgment of the investigator.

Important Medical Events are considered to be of significant medical magnitude (based on medical judgment) such that the event may jeopardize the subject to an extent that it may require medical or surgical intervention to prevent one of the outcomes listed as an SAE. Examples of such medical events include, allergic bronchospasm requiring intensive treatment in an emergency room or at home, blood dyscrasias or convulsions that do not result in hospitalization, or development of drug dependency or drug abuse.

The seriousness criterion of "medically significant" should only be selected when none of the other seriousness criteria apply to the event but the Investigator still considers the event as serious.

An 'unexpected' adverse event is one not identified in nature, severity, or frequency in the investigator's brochure or the product package insert for the study drug.

## 9.5.2. Intensity (severity)

The intensity of each AE must be assessed by the Investigator using one of the following categories and recorded in the subject's Case Report Form (CRF).

# Description of Intensity (severity) of Adverse events

The NCI Common Terminology Criteria for Adverse Events version 5.0 (Current version) is a descriptive terminology which can be utilized for Adverse Event (AE) reporting. A grading (severity) scale is provided for each AE term.

## Adverse Event Terms

An AE is any unfavorable and unintended sign (including an abnormal laboratory finding), symptom, or disease temporally associated with the use of a medical treatment or procedure that may or may not be considered related to the medical treatment or

procedure. An AE is a term that is a unique representation of a specific event used for medical documentation and scientific analyses.

## **Serious Suspected Unexpected Adverse Reaction (SUSAR)**

An unexpected adverse reaction (UAR) is an adverse reaction that is not consistent with the product information in the IB/SmPC. A suspected unexpected serious adverse reaction (SUSAR) is any UAR that at any dose:

- Results in death;
- Is life threatening (i.e. the subject was at risk of death at the time of the event; it
  does not refer to an event which hypothetically might have caused death if it were
  more severe);
- Requires hospitalisation or prolongation of existing hospitalisation;
- Results in persistent or significant disability or incapacity;
- Is a congenital anomaly or birth defect.
- Medically significant

## **Adverse Drug Reaction (ADR)**

An ADR is any untoward and unintended response to an IMP related to any dose administered. The definition implies a reasonable possibility of a causal relationship between the AE and the IMP. This means that there are facts (evidence) or arguments to suggest a causal relationship, the relationship cannot be ruled out.

#### **Medical Event:**

A medical event is defined as any untoward medical occurrence in a patient or a healthy volunteer after signing the ICF till the administration of the first dose of the investigational medicinal product.

An SAE which occurs before administration of study drug (e.g. during screening) will not be considered for expedited reporting to the authorities.

An SAE which occurs as a result of any screening procedure will also not be considered for expedited reporting to the authorities but will be entered in the subject's source records and the CRF.

## Grades of Severity

Grade refers to the severity of the AE. In oncology studies as an example, The CTCAE v 5.0 displays Grades 1 through 5 with unique clinical descriptions of severity for each AE based on this general guideline:

- Grade 1 Mild AE
- Grade 2 Moderate AE
- Grade 3 Severe AE
- Grade 4 Life-threatening or disabling AE
- Grade 5 Death related to AE

## 9.5.3. Causality assessment

The Investigator will assess the causality / relationship between the study drug and the AE and record that assessment in the subject's enrollment Case Report Form (CRF).

Description of causal relationship of adverse events to the study drug regimen:

**Definite:** The event occurred with a plausible time relationship to medicine use; it could not be explained by concurrent diseases, or other medicines or substances; Withdrawal of the medicine resulted in recovery or significant improvement, and re-initiation ("rechallenge") of the medicine, if it was appropriate, resulted in recurrence of the same event; and the event was a recognizable pharmacological action of the medicine or a clearly identifiable clinical event.

**Probable:** means the occurrence of the event was temporally associated with administration of the medicine, it was unlikely to be caused by a concurrent disease or other medicine or substance, and withdrawal of the medicine resulted in improvement or recovery.

**Possible:** means the occurrence of the event was temporally associated with administration of the medicine, but it could also be explained by concurrent disease or other medicine or substance, and/or details such as administration dates or response to withdrawal of the medicine may have been absent or unclear.

**Unlikely:** means the event occurred at a time in relation to medicine administration, which made causation improbable. Concurrent disease or other medicine or substance may have provided a plausible explanation.

**Unclassified:** means more data were required in order to assess the adverse event.

**Unclassifiable:** means the data available were insufficient or contradictory, and it was not possible to obtain further data or verify existing data.

## 9.6. Recording of Adverse Events

Adverse event reporting will extend from signing of informed consent until Visit 5/Early Termination visit. All AEs, regardless of the relationship to study drug, will be recorded in the subject's Case Report Form (CRF).

The Investigator will record all AEs, regardless of relationship to study drug on the adverse event page in the in the subject's Case Report Form (CRF). Standard medical terminology should be used when describing AEs. Whenever possible a diagnosis should be made and recorded on the CRF rather than listing signs and symptoms. Intermittent AEs can be recorded once. The anatomical location of the AEs must be specified where applicable.

The following information should be recorded in the subject's Case Report Form (CRF).

## **Description:**

- Severity of the event (see Intensity for details)
- Study drug use continued or not
- Outcome of the event (resolved, persistent, unknown, death)
- Relationship to study drug (see Relationship to Study drug (Causality) for details)
- Indication of whether the event is serious (see Seriousness for details)
- Actions taken including treatment with concomitant medication

#### 9.6.1. Procedures for Reporting of Adverse Events

All serious adverse event (SAE) that occur during the study period, whether or not considered to be related to the study drug, must be reported (typed in English) to the Sponsor, within 24 hours of the information becoming available.

These SAE reports must contain the following information:

- A. Study name/number
- B. Study Drug
- C. Investigator details (name, phone, fax, e-mail)
- D. Subject Number
- E. Subject Initials
- F. Subject Demographics
- G. Clinical Event
- 1) Description
- 2) Date of onset
- 3) Treatment (drug, dose, dosage form)
- 4) AE Relationship to study drug
- 5) Action taken regarding study drug in direct relationship to the AE
- 6) Results of tests or investigations, which are relevant for interpretation of SAE
- 7) Outcome of the event (Recovered/ recovered with sequelae, Not recovered, Recovering)
- H. If the AE was fatal
- 1) Cause of death (whether or not the death was related to study drug)
- 2) Autopsy findings (if available)

The SAE form completion and reporting must not be delayed even if all of the information is not available at the time of the initial contact. Additional information (follow-up) about any SAE unavailable at the initial reporting should be forwarded within 24 hours of the information becoming available. Subjects who have had an SAE during the treatment period must be followed clinically until all parameters (including laboratory) have either returned to normal or have stabilized or are otherwise explained.

#### 9.7. Reporting of Serious Adverse Events

The CDSCO, in pursuance to implementation of the e-Governance has launched various online services through the portal "SUGAM" (www.cdscoonline.gov.in) on 14.11.2015. The stakeholders were requested to avail this facility which is intended to further reduce

Dr.Reddy's

the time and transaction cost. Therefore, it is effective from 14.03.2021, and from this date online files of SAE reports were to be sent for processing through SUGAM portal.

All SAEs should be reported to Central Licensing Authority via SUAGM portal.

All SAEs should be reported by the investigator to the Licensing authority (via SUGAM portal), Sponsor and to the Ethics Committee that accorded approval to the study

protocol within 24 hours of their occurrence/awareness

Investigator must notify all the SAEs to the sponsor representatives listed below via

email or fax:

Sponsor contact:

[contact]

Email ID: [contact]

**AND** 

[contact]

If the outcome of the SAE is fatal i.e. SAE results in death, the report on SAE of death after due analysis (Table 5 of schedule III of New Drugs and Clinical Trials Rules 2019

G.S.R. 227(E)) shall be submitted by the investigator to the DCGI (Central Licensing Authority) via SUGAM portal, the Chairman of the ethics committee that accorded permission to conduct the study, and to the Head of the institution where the trial has been conducted, within 14 calendar days of knowledge of occurrence of the SAE.

The Central Licensing Authority should forward the report of the Investigator, Sponsor or its representative (whosoever had obtained permission from the Central Licensing Authority for conducting clinical trial) and the Ethics Committee to the Chairperson of the Expert Committee.

If the SAE is permanent disability or any other injury other than death, the reports (Table 5 of schedule III of New Drugs and Clinical Trials Rules 2019 G.S.R. 227(E)) on SAE, after due analysis should be submitted by the investigator to the DCGI (Central Licensing authority) via SUGAM portal, the chairperson of ethics committee and to

Head of the institution where the trial has been conducted, within 14 calendar days (or as per applicable regulatory timelines) of reporting of the event.

In case of a serious adverse event of death, the sponsor or its representative shall forward the reports on SAE after due analysis to the DCGI (Central Licensing authority) via SUGAM portal, Chairperson of the Ethics committee, and Head of the institution, where the trial has been conducted within 14 calendar days of knowledge of occurrence of the SAE.

In case of any SAE of permanent disability or any other injury other than deaths, the sponsor or its representative shall forward the reports on SAE after due analysis to the DCGI (Central Licensing authority) via SUGAM portal, Chairperson of the Ethics committee, and Head of the institution, where the trial has been conducted within 14 calendar days of reporting of SAE.

All SAE reports shall be submitted to the DCGI as per – table 5 of schedule III of New Drugs and Clinical Trials Rules 2019 G.S.R. 227(E), in accordance with the format and checklist (based on the event). The sponsor will submit all SAE report to CDSCO via SUGAM portal as per table 5 of schedule III of New Drugs and Clinical Trials Rules 2019 G.S.R. 227(E). The sponsor or its representative shall submit all SAE reports to CDSCO as per table 5 of schedule III of New Drugs and Clinical Trials Rules 2019 G.S.R. 227(E). The SAE reports will be submitted with proper binding, indexing and page number.

Sponsor shall share the due analysis report with all other participating Investigator(s) / study site team(s) and same has to be notified by site team(s) to their respective IECs

All adverse events, independent of relationship to study drug, must be reported starting from time of first administration of study drug until end of study or early termination. Subjects will be followed-up for adverse events until complete resolution.

All SAEs will be followed until resolution, stabilisation, until the event is otherwise explained, or the patient is lost to follow-up.

A event which occurs before administration of study drug/procedure (e.g. during screening/as a result of screening, after signing the ICF and before administration of the study drug, during check-in/after check-in and before administration of the study drug)

will not be considered as adverse event for the investigational product and hence it will not be reportable as adverse event for the investigational product to the applicable regulatory authorities (e.g. DCGI, etc.).

If there is any change in the Pharmacovigilance regulation by the DCGI (licensing authority) in regard to the SAE reporting, the timelines for SAE reporting, the concerned authorities/ personnel to whom the SAE's has to be reported then the applicable Pharmacovigilance regulations will be followed by Investigator / Sponsor. The investigator / Sponsor will comply to the changes in the Pharmacovigilance regulations (SAE reporting and timelines for SAE reporting), by the DCGI (licensing authority) on their responsibilities. The investigator will cooperate with the sponsor in complying to the change in the Pharmacovigilance regulation (SAE reporting and timelines for SAE reporting), as applicable.

Serious adverse event (SAE) occurring during a clinical trial should be communicated promptly (within 14 calendar days) by the Sponsor or its representative to the other Investigator(s) participating in the study.

Investigator Reporting of Pregnancy - Notifying the Study Sponsor

All patients who participate in the study should be counselled on the need to practice adequate birth control and on the importance of avoiding pregnancy during study participation as detailed in the inclusion and exclusion criteria. Serum pregnancy testing will be performed at screening. A subject who is found to be pregnant at the screening visit will be excluded from the study and will be a screening failure. Patients who have been enrolled in the study should be instructed to contact the Investigator or study staff immediately if pregnancy occurs or is suspected. Early termination visit assessments are required as soon as possible after learning of the pregnancy. Pregnant females will be discontinued from study treatment by the Investigator. A male that has a partner that becomes pregnant during the study will not be discontinued from study treatment, however the pregnancy will be reported and documented. Urine pregnancy will be performed at subsequent visits, if applicable.

Details of the pregnancy should be recorded on the Pregnancy Report form and reported [name] Limited within 24 hours of awareness by email

[contact] from the time of initial awareness, even if beyond the closure of the clinical database.

# 9.7.1 Compensation in case of injury or death during clinical trial

In case of an injury occurs to any subject during clinical trial, the sponsor, shall provide the cost for medical management to such subject as long as required as per the opinion of investigator or till such time it is established that the injury is not related to the clinical trial, as the case may be, whichever is earlier.

In case of clinical trial related death or permanent disability or any other injury other than deaths, the sponsor or its representative shall pay the quantum of compensation as decided by the Central Licensing Authority, within thirty days of the receipt of such order.

In the event of an injury, not being permanent nature, the quantum of compensation shall be commensurate with the loss of wages of the subject as provided in the seventh schedule of The New Drugs and Clinical Trials Rules 2019 G.S.R. 227(E).

In case of permanent disability or any other injury occurs to any subject during clinical trial, the trial subject shall be provided financial compensation by the sponsor or its representative, as per order of the Licensing Authority defined under sub rule 3 of rule 42 of chapter VI of New Drugs and Clinical Trials Rules 2019 G.S.R. 227(E), and the financial compensation shall be in addition to any expenses incurred on the medical management of the trial subject.

In the case of death occurs to the trial subject during clinical, his/her nominee(s) should be entitled for financial compensation by the sponsor or its representative, as per the order of the Central Licensing Authority defined under sub rule 2 of rule 42 of chapter VI of New Drugs and Clinical Trials Rules 2019 G.S.R. 227(E), and the financial compensation shall be in addition to any expenses incurred on the medical management of the trial subject

Known Adverse Events with the study drug

In CIC clinical trials, the most common adverse reactions in LINZESS-treated patients (incidence  $\geq$ 2% and greater than placebo) were (i) diarrhea (16% vs 5% placebo), (ii) abdominal pain (7% vs 6%), (iii) flatulence (6% vs 5%), (iv) upper respiratory tract

infection (5% vs 4%), (v) sinusitis (3% vs 2%) and (vi) abdominal distension (3% vs 2%).

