### 1.2 Approved Product Information as per PMDA label

Active ingredient: Elobixibat 5 mg in 1 tablet (5.13 mg as Elobixibat hydrate)

Additive: Crystalline cellulose, D-mannitol, hypromellose, sodium croscarmellose, light anhydrous silicic acid, magnesium stearate, macrogol 6000, titanium oxide, yellow iron sesquioxide, carnauba wax.

Elobixibat was jointly developed by EA Pharma and Mochida. EA Pharma and Mochida distribute elobixibat under the same brand name "GOOFICE 5mg Tablet", respectively, in Japan. 

Chemical name: [(2 R) -2- (2-{[3, 3-Dibutyl-7-(methylsulfanyl) -1,1-dioxo-5-phenyl-2,3,4,5-tetrahydro-1 H -1, 5-benzothiazepin-8-yl] oxy} acetamide) -2-phenylacetamido] acetic acid monohydrate.

Molecular formula: C 36 H 45 N 3 O 7 S 2 • H 2 O

Properties: Elobixibat hydrate is a white powder. This product is freely soluble in N, N -dimethylformamide, sparingly soluble in acetonitrile or methanol, sparingly soluble in ethanol (99.5), and practically insoluble in water.

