# Side effects:

The following side effects may occur, so observe carefully and take appropriate measures such as discontinuing administration if any abnormalities are observed.

	5% or more	Less than 1-5%	Less than 1%	Frequency unknown
Liver		Liver dysfunction (ALT increased, AST increased, γGTP increased, AIP increased, LAP increased)		
Psycho-nervous system		Floating dizziness		Headache
Cardiovascular				Hot flashes
Digestive organ	Abdominal pain (23.2%), diarrhea (14.4%)	Lower abdominal pain, bloating, nausea, upper abdominal pain, abdominal discomfort, loose stools.	Mouth ulcer, dry mouth	Flatulence, urgency, vomiting, abnormal gastrointesti nal sounds, constipation
Hypersensitivity			Urticaria	rash
blood		Anemia	Increased vitamin E	Increased eosinophil count
others		CK increase		Dysmenorr hea

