#### 12. INVESTIGATIONAL PRODUCT MANAGEMENT

#### 12.1. Study Drugs

**Test drug:** Elobixibat 5 mg

**Comparator:** Placebo matching Elobixibat 5 mg tablet

The sponsor will supply the study drugs to the investigators duly labeled and packed. The sponsor will supply rescue medicine but not the concomitant medication.

**Method of assigning treatment**: Eligible subjects after confirmation of diagnosis and conformance with entry criteria will be randomized to any of the treatment groups. Study Medication will be dispensed to the randomized subjects.

**Storage conditions:** All study drug supplies will be stored as per COA or as per sponsor's / manufacturer's instructions. Until dispensed to the subjects, the study drug will be stored in a secure, temperature controlled, restricted access area accessible to authorized personnel only.

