## 13.3.2. Safety Analysis

The safety analysis will be performed using the Safety Population. The safety parameters include AEs, clinical laboratory parameters, vital signs, and ECG parameters. For each safety parameter, the last assessment made before randomization will be used as the baseline for all analyses of that safety parameter.

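### Section 9.7.1 presents another product's adverse events as those of the study drug and conflicts with section 1.2; separately, Table 1 and section 7.1.4 disagree on the Visit 4 ECG that the safety analysis uses

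*Protocol*

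**What the plan says.** **Adverse-event profile.** Section 12.1 names the product under test: "Test drug: Elobixibat 5 mg". Section 1.2 says that its two marketing companies "distribute elobixibat under the same brand name 'GOOFICE 5mg Tablet", and no other brand name for elobixibat appears in the protocol. The side-effect table in 1.2 has two entries in its highest frequency band: "Abdominal pain (23.2%), diarrhea (14.4"%). The next band down includes liver enzyme rises and CK increase.

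The closing paragraph of 9.7.1, a section otherwise about compensation for injury, is headed "Known Adverse Events with the study drug". Its first sentence concerns "In CIC clinical trials, the most common adverse reactions in LINZESS-treated patients". The first two rates it gives are "i) diarrhea (16% vs 5% placebo") and "ii) abdominal pain (7% vs 6"%). Flatulence, upper respiratory tract infection, sinusitis and abdominal distension follow.

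**ECG.** Table 1 marks the 12-lead ECG at Visit 1 and at no later visit. Section 7.1.4 includes it among the procedures for patients who complete treatment. Section 13.3.2 states: "The safety parameters include AEs, clinical laboratory parameters, vital signs, and ECG parameters". Section 6.2 names the same parameters. In both sections the baseline is the latest value before randomisation.

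**The concern.** A protocol should give one answer to the question of what is known about the drug's side effects. This one gives two, and the paragraph explicitly labelled as the study drug's profile is the wrong one. It sits in the adverse-event chapter, and the protocol goes to ethics committees. A reader who stops there would take abdominal pain to be barely more frequent than on placebo, whereas 1.2 makes it the most frequent side effect.

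The ECG problem is a separate one. An analysis against a pre-randomisation baseline needs a later value. If some sites follow the schedule table and others the visit text, ECG would be missing by site, according to which page each site used. The three changes logged for Version 2.0 touch neither point.

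**Working it through.** **1. Does the 9.7.1 paragraph describe the study drug?** The two lists side by side:

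| Event | 9.7.1 (LINZESS vs placebo) | 1.2 (elobixibat) |
|---|---|---|
| Abdominal pain | 7% vs 6% | 23.2% |
| Diarrhea | 16% vs 5% | 14.4% |
| Upper respiratory tract infection | 5% vs 4% | not listed |
| Sinusitis | 3% vs 2% | not listed |
| Liver enzyme rises | not listed | listed, band up to 5% |
| CK increase | not listed | listed, band up to 5% |

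The product name differs from the only brand name given for elobixibat, and the figures differ too. The paragraph therefore cannot be read as elobixibat data under another trade name.

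**2. Size of the disagreement.** Inputs: the rates above and 75 subjects per arm (13.2). Formulas: ratio = rate in 1.2 / rate in 9.7.1; expected cases = n × p. The assumption, for scale only, is that each rate carries over to 75 treated subjects in this two-week trial.

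- Abdominal pain, ratio: 23.2 / 7 = 3.3.
- Abdominal pain, expected cases: 75 × 0.07 = 5.3 against 75 × 0.232 = 17.4.
- Diarrhea, ratio: 14.4 / 16 = 0.9.
- Diarrhea, expected cases: 75 × 0.16 = 12.0 against 75 × 0.144 = 10.8.

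The conflict is material for abdominal pain and slight for diarrhea.

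**3. ECG, place by place.**

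| Place | ECG at screening | ECG at Visit 4 |
|---|---|---|
| Table 1 | yes | no |
| 7.1.1 (Visit 1 text) | yes | – |
| 7.1.4 (Visit 4 text) | – | yes |
| 6.2 and 13.3.2 | needed as baseline | needed as the value to compare |

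In Table 1 the physical examination and laboratory rows keep their second mark at Visit 4. The single mark in the ECG row is therefore unlikely to be an artefact of reading the PDF.

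**4. Bounds on post-baseline ECGs among the 150 randomised.**

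- Every site works from Table 1 alone: 0.
- Every site works from 7.1.4 and no withdrawn subject attends an early-termination visit: at the planned drop-out of about 20%, 150 × (1 − 0.20) = 120.
- Every site works from 7.1.4 and all withdrawn subjects attend: 150.

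The documents do not show how sites would divide between table and text, so no point estimate is possible.

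**The case against.** **The protocol does carry the correct profile.** Section 1.2 has the full elobixibat table, and 8.2 warns of abdominal pain and diarrhea. Liver function is tested at screening and end of trial, and all adverse events are recorded whatever their relationship to the drug. Section 9.5.1 ties unexpectedness to the investigator's brochure or package insert, and the SUSAR text ties it to the IB or SmPC. No assessment or reporting rule points to the 9.7.1 paragraph, which names the other product openly. All of this stands, and it limits the harm.

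**A reader might infer that investigators will judge causality from the wrong drug's profile.** The documents do not support that. The categories in 9.5.3 rest on timing, alternative explanations and response to withdrawal or rechallenge. The top category also asks whether the event is a recognisable pharmacological action, but none refers to 9.7.1.

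**The ratio of 3.3 compares two products.** The table in 1.2 gives no placebo rate, treatment duration or trial setting, and 9.7.1 lists only the commoner reactions. The ratio shows that the text belongs to another product; it does not measure damage to this trial.

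**A reader might also infer that the ECG analysis cannot be carried out.** That does not follow. Section 7.1.4 requires the ECG of completers, and 5.3 and 7.2 extend Visit 4 procedures to subjects who withdraw. With the screening ECG as baseline, the protocol as a whole provides both values. Zero of 150 is the extreme in which every site ignores the visit text.

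**Conclusion.** Both inconsistencies are on the face of the protocol and should be corrected.

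- **Adverse-event profile:** 9.7.1 attributes another product's adverse events to the study drug and contradicts 1.2. The clearest case is abdominal pain, by a factor of 3.3, together with the omitted liver enzyme and CK rises and the two added respiratory events. The practical effect is limited, because the correct profile and the expectedness reference are stated elsewhere.
- **ECG:** the Visit 4 ECG is missing from Table 1 but not from the protocol. The supportable risk is uneven collection between sites and an incomplete ECG safety analysis, of unknown extent.

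The two points are unrelated to each other. Neither affects the primary efficacy analysis, the type I error or the sample size. The conclusion assumes that the ECG row of Table 1 was read correctly from the PDF. The expected case counts also assume that the quoted rates transfer to this trial, but the contradiction itself does not depend on that.

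**What to change.** 1. In 9.7.1, replace the LINZESS paragraph with the elobixibat side-effect data already in 1.2, or with a reference to that table. Place it in the adverse-event text rather than at the end of the compensation section.
2. Reconcile the 12-lead ECG row of Table 1 with 7.1.4, so that the analysis in 13.3.2 has a post-baseline value to set against the screening ECG.

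The cost is one short amendment and a memo to sites. If the reconciliation keeps what 7.1.4 already lists, no procedure is added.
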